13.1.1 Deviations From Non-Informative Censoring

One of the assumptions underlying the primary analysis is that the censoring mechanism is non-informative. In order to assess the sensitivity of the primary analysis to deviations from this assumption, a reference-based multiple imputation method will be used (Lu et. al., 2015). Subjects who don't relapse but who discontinue from the study prior to the Week 26 assessment, for any reason other than termination of the study by the sponsor, will have time to relapse values imputed conditionally on their observed censored values. Censoring due to completion of the 26 week double-blind period, study being terminated by the sponsor or ongoing at the time of the interim analysis datacut (for the interim analysis only), will be treated as non-informative and no imputation will be performed for these subjects. The

imputation algorithm will be based on the assumption that the risk of relapse (i.e. hazard rate) for pimavanserin subjects who prematurely discontinue is the same as that for placebo subjects. If the imputed event time exceeds the applicable cutoff date for a planned analysis, or the date corresponding to Week 26 for the subject, whichever comes first, the time-to-event will be right censored at the earlier of the two dates. Random number seeds of 201938 and 202075 will be used for the posterior draw of model parameters from the imputation model and for imputation of censored event times, respectively. A total of 1000 imputed datasets will be created.

The imputation model will be a Cox regression model with piecewise exponential baseline hazards fit to the ITT Analysis Set with treatment, designated dementia subtype, and region as covariates. A noninformative improper prior for the baseline hazard parameters and an improper uniform prior for the regression coefficients will be assumed. For the piecewise constant baseline hazards, the post-baseline follow-up time axis will be partitioned into 2 disjoint intervals, where the interval cut-points will be such that there will be a similar amount of relapse events in each interval. Sampling of model parameters will set the burn-in to 200 and every 10th sample will be kept. [REDACTED]

[REDACTED]

When imputing censored event times, posterior samples for the treatment parameter will be set to 0 so that the assumption that the risk of relapse (i.e. hazard rate) for pimavanserin subjects who prematurely discontinue is the same as that for placebo subjects. Additional details of how censored event times will be imputed can be found in Lu et. al. (2015). If the imputation model cannot be fit due to sparse covariate data, this will be documented and the imputation model will be modified to include only treatment as a covariate.

For each of the 1000 imputed datasets, a Cox regression model with effects for treatment group, designated dementia subtype, and region will be used to obtain an estimate of the log

hazard ratio and associated standard error. These estimates will be combined using Rubin's rule to obtain an overall hazard ratio, standard error, 95% confidence interval, and p-value (Rubin, 1976).

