1.3.1 Parkinson's Disease Psychosis Program

The scope of the development program for pimavanserin is the largest ever conducted in PDP. At the time of approval, 616 mostly older, late-stage PDP subjects had been evaluated in 16 countries over a span of >10 years. Clinically meaningful efficacy was established in Study ACP-103-020, a 6-week, placebo-controlled Phase 3 study (Cummings et al. 2014). This efficacy was supported by data from additional short-term Phase 2b/3 studies. In ACP-103-020, pimavanserin 34 mg consistently demonstrated statistically significant efficacy across multiple and independent endpoints, subject subgroups, and sensitivity analyses. Improvements in sleep and daytime wakefulness were also observed. These clinical

benefits were achieved without worsening of Parkinson's disease motor symptoms and without a number of other safety concerns associated with atypical antipsychotics.

Pimavanserin is considered to be generally safe and well tolerated. Across all clinical studies of pimavanserin, the most frequently reported treatment-emergent adverse events (TEAEs) were in the central nervous system (CNS), gastrointestinal, and psychiatric systems. Most events were mild to moderate in intensity. The most common CNS TEAEs included dizziness (including postural), headache, and somnolence (drowsiness). Common gastrointestinal disturbances included dyspepsia, nausea, constipation, and vomiting. Severe nausea and vomiting were dose limiting in a few cases. Reported psychiatric conditions included agitation, insomnia, and confusional state.

Clinical and nonclinical safety pharmacology studies of pimavanserin suggest a potential risk for QT prolongation. The magnitude of effect in humans has been assessed in a thorough QT study with doses of pimavanserin ranging from 17 to 68 mg. In the Phase 3 PDP program, an average prolongation of approximately 5 to 8 ms was observed with pimavanserin 34 mg.

The US package insert for pimavanserin has a boxed warning that elderly patients with dementia-related psychosis treated with antipsychotic drugs are at an increased risk of death. Pimavanserin is not approved in the treatment of patients with dementia-related psychosis unrelated to the hallucinations and delusions associated with Parkinson's disease psychosis.

Additional information is provided in the pimavanserin Investigator's brochure and in the NUPLAZID[®] (pimavanserin) US package insert.

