NPI-NH psychosis score responder analyses also demonstrate the significant and clinically relevant treatment effect of pimavanserin 34 mg compared with placebo in subjects with ADP. Furthermore, defining responder as either a 30% or greater improvement or a 50% or greater improvement from Baseline NPI-NH psychosis score showed a significantly greater proportion of responders in the pimavanserin group (Table 1–2).

Table 1–2 NPI-NH Psychosis Score Percent Responder Analysis – Full Analysis Set – Week 6 (Day 43)

Treatment Group (% Responder)	Percent Improvement from Baseline				
	≥20%	≥30%	≥50%	≥75%	100%
Pimavanserin 34 mg	58.6%	55.2%	50.6%	27.6%	12.6%
Placebo	46.2%	37.4%	34.1%	16.5%	9.9%
p-value for test of group difference	0.0937	0.0159	0.0240	0.0656	0.5514

Source: ACP-103-019 Clinical Study Report

Note: Missing values were imputed as non-response

With respect to safety, pimavanserin appeared to be well-tolerated with no new safety observations in this elderly and frail patient population compared to the pimavanserin PDP safety database. An equal number of post-randomization deaths were reported: 4 deaths in the pimavanserin group and 4 in the placebo group.

There were more SAEs reported in pimavanserin group (16.7%) than in the placebo group (11.0%). A review of individual SAEs revealed a similar distribution of Medical Dictionary for Regulatory Activities (MedDRA) preferred terms between the two treatment groups with no clusters or common underlying mechanisms identified. However, there were fewer

discontinuations due to AEs in the pimavanserin group (8.9%) compared with the placebo group (12.1%).

The most frequently reported AEs in the pimavanserin group were fall (23.3%), urinary tract infection (22.2%), and agitation (21.1%). Agitation was reported more often in the pimavanserin group than in the placebo group.

The mean change from baseline in the QTc interval in subjects treated with pimavanserin was 9.4 ms at 12 weeks (Day 85) with no significant outliers reported at Day 85 (>500 ms or $\Delta \geq 60$ ms). One subject in the pimavanserin group and one subject in the placebo group had a $\Delta \geq 60$ ms at Day 15. Each subject continued in the study.

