4.4 Subject Withdrawal or Termination

In accordance with the Declaration of Helsinki and other applicable regulations, a subject has the right to withdraw from the study at any time, and for any reason, without prejudice to his or her future medical care.

Subjects may be discontinued or withdrawn from the study for a number of reasons, including, but not limited to, those listed below:

- Relapse of hallucinations and delusions associated with dementia-related psychosis
- Adverse event
- Death
- Lost to follow-up
- Non-compliance with study drug
- Use of prohibited medications
- Physician decision
- Pregnancy
- Protocol violation
- Study terminated by Sponsor
- Subject withdraws consent
- Other

When a subject is found to be appropriate for discontinuation from the trial, the visit during which this is determined should immediately be converted to an ET visit (as described in [Table S-2](#)) and all procedures and assessments listed in the schedule of events for the ET visit (Week 38/EOT; Visit 17/ET) should be completed. Safety follow-up should be completed as scheduled.

For subjects who discontinue from the trial between visits, every reasonable effort should be made to complete Visit 17/early termination (ET) and the safety follow-up period.

If a subject is lost to follow-up, every reasonable effort should be made to phone the subject approximately 4 weeks after last known contact with the subject in order to assess the subject's current status. All phone contact with the subject should be documented.

For subjects who continue to be followed for safety, SAEs should continue to be reported as described in [Section 7.4.2](#).

If a subject is discontinued from the study because of an AE, every reasonable attempt should be made to follow the subject until the AE resolves or until the Investigator deems the AE to be chronic or stable.

All SAEs will continue to be followed until such events have resolved or the Investigator deems them to be chronic or stable.

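### The informative-censoring sensitivity analysis (SAP 13.1.1) does not cap imputed relapse times at death, so it can date relapses after a subject has died

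*SAP*

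**What the plan says.** SAP 13.1.1 applies to subjects without a relapse "who discontinue from the study prior to the Week 26 assessment, for any reason other than termination of the study by the sponsor". These subjects "will have time to relapse values imputed conditionally on their observed censored values". The hazard used is that of placebo in both arms, because "posterior samples for the treatment parameter will be set to 0".

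Three kinds of censoring are excepted: completing the 26 weeks, termination of the study by the sponsor, and being ongoing at the interim cut. These "will be treated as non-informative and no imputation will be performed for these subjects". Draws that run past the analysis cutoff or the subject's Week 26 are truncated: "the time-to-event will be right censored at the earlier of the two dates". No other cap is given.

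Death is one of the reasons under Protocol 4.4, in the list introduced by "Subjects may be discontinued or withdrawn from the study for a number of reasons, including, but not limited to, those listed below". SAP 6.2 and 13.2 also list it as a double-blind discontinuation reason, and SAP 6.2 lists it separately from sponsor termination. SAP 5.2.3 censors non-relapsers at their last applicable SAPS-H+D assessment, so a death without relapse is censored on or before the day of death.

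**The concern.** The placebo-hazard assumption makes sense for a living subject who has stopped drug. It has no meaning after death, when relapse is impossible. Read as written, the rule handles a death like a withdrawal of consent. The draw starts at the last SAPS-H+D assessment and may run through the death date up to Week 26. The result is either a relapse that cannot have happened or a deceased subject who stays in the risk set.

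The relapse sensitivity analyses in 13.1.2 vary the source of events, the cutoff and the analysis set. None treats death separately. At stake is what the 13.1.1 result means: if deaths are not rare, it mixes mortality with loss of efficacy and a reader cannot separate the two. Protocol 1.3.1 reports a boxed warning that "elderly patients with dementia-related psychosis treated with antipsychotic drugs are at an increased risk of death", so the SAP should say how deaths are handled.

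**Working it through.** **Inputs.** From SAP 3.4: relapse 60% on placebo and 35% on pimavanserin, and drop-out 25%, all over 26 weeks; 89 per arm; 75 events. With 26 weeks as the time unit and constant hazards:
- placebo relapse: −ln(0.40) = 0.916
- pimavanserin relapse: −ln(0.65) = 0.431
- drop-out δ: −ln(0.75) = 0.288

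**Reproducing the plan.** The hazard ratio is 0.431/0.916 = 0.470. Schoenfeld's formula at the final-look level of 0.0479 (two-sided) with 90% power gives 75 events. The chance of an observed relapse is λ/(λ+δ) × (1 − e^−(λ+δ)), which is 0.533 on placebo and 0.307 on pimavanserin. Then 89 × (0.533 + 0.307) = 74.8 events. The design figures hold.

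**How much is imputed.** Drop-outs before relapse are 89 × δ/(λ+δ) × (1 − e^−(λ+δ)), which is 14.9 on placebo and 18.3 on pimavanserin, about 33 in all. Imputing them at the placebo hazard to Week 26 adds 6.0 + 6.9 = about 13 relapses per dataset.

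**One subject who dies.** For a death at double-blind week w, with censoring taken at death, the chance of an imputed relapse before Week 26 is 1 − 0.40^((26−w)/26):

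| Week of death | 4 | 8 | 13 | 18 | 22 |
|---|---|---|---|---|---|
| Chance | 54% | 47% | 37% | 25% | 13% |

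Averaged over time of death this is about 39%. The other 61% or so stay at risk to Week 26.

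**Across the trial.** The documents give no death rate for this study, so q, the 26-week death risk, is an assumption. The upper end comes from the Phase 2 study in Protocol 1.3.2, which had "4 deaths in the pimavanserin group and 4 in the placebo group" among 181 randomized. Taking those deaths to have occurred over that study's 12 weeks (also an assumption) gives 1 − (1 − 8/181)^(26/12) = 9.3%. Deaths are counted inside the 25% drop-out, with hazard −ln(1−q) in each arm. Hazard ratios come from a large simulation (2 million subjects) of the imputation, with deaths imputed and then with deaths censored at death.

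| q | Deaths before relapse, placebo + pimavanserin | Imputed relapses in these subjects | HR, deaths imputed | HR, censored at death |
|---|---|---|---|---|
| 1% | 0.52 + 0.64 = 1.2 | 0.21 + 0.24 = 0.5 | 0.525 | 0.523 |
| 2% | 1.05 + 1.28 = 2.3 | 0.42 + 0.49 = 0.9 | 0.525 | 0.522 |
| 5% | 2.65 + 3.26 = 5.9 | 1.07 + 1.24 = 2.3 | 0.523 | 0.513 |
| 9.3% | 5.07 + 6.22 = 11.3 | 2.04 + 2.36 = 4.4 | 0.526 | 0.508 |

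The fourth column varies only through simulation error. The primary analysis stays at about 0.47 throughout.

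**Unequal deaths.** With 9.3% on pimavanserin and 2% on placebo, the hazard ratio is 0.526 with deaths imputed and 0.509 without. With the risks reversed it is 0.526 and 0.522. In every case run, the present rule gives the higher figure.

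**Relapse or death as one event.** Under constant hazards, the 9.3% versus 2% case gives (0.431 + 0.098)/(0.916 + 0.020) = 0.529/0.936 = 0.565. A composite therefore shows an excess of deaths on pimavanserin more plainly than either imputation rule.

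**The case against.** The strongest reply is that this is one sensitivity analysis, that it errs against the drug, and that removing deaths from the imputation would soften it exactly when deaths are in excess on pimavanserin. With deaths added on top of the 25% drop-out, at assumed risks of 9% on pimavanserin and 3% on placebo, a simulation gives about 0.55 under the present rule and about 0.53 without deaths (error about 0.01). This stands, and it is why a cap at death should not be adopted alone.

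Two further points stand. Censoring deaths at the death date throughout would conflict with SAP 5.2.3, which uses the last SAPS-H+D assessment. And because the draw starts at that assessment, some imputed relapses fall before death: at the top death rate about 1.9 and 2.2 per arm fall after it, against the 2.0 and 2.4 above.

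Readers might also infer more than the documents support:
- *That every subject who dies is given a relapse.* About 39% are, per dataset.
- *That deaths are counted nowhere.* The key secondary endpoint counts them as discontinuation events under type I error control. SAP 13.2 tabulates them by arm, SAP 14.1 summarizes fatal adverse events, and the adjudication committee reviews every double-blind early termination before the study discontinuation date, so a relapse preceding a death can be captured.
- *That the Phase 2 rate applies here.* Those were nursing-home residents with a mean age of 85.9 years. This trial excludes hospice, bed-bound and skilled-nursing subjects and randomizes only 12-week responders. The Phase 2 deaths were also equal in number, 4 and 4.

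Part of 13.1.1 is blacked out after the sampling settings, and further imputation detail is left to a cited paper. An exception for deaths there cannot be excluded, but the readable list of exceptions has none.

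**Conclusion.** The gap is real and narrow. As written, 13.1.1 allows imputed relapses, and time at risk, after death. For assumed 26-week death risks of 1% to 9.3%, about 0.5 to 4.4 of some 13 imputed relapses per dataset (0.5/12.9 = 4% to 4.4/12.9 = 34%) belong to subjects who died. The illustrative hazard ratio falls by about 0.002 to 0.018 when they are not imputed. These figures rest on constant hazards, the design relapse and drop-out rates, deaths lying within the 25% drop-out, and censoring at death.

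A reader might infer that the primary result is compromised, or that the rule could produce a false claim of efficacy. Neither follows. The primary analysis censors these subjects and imputes nothing. When pimavanserin lowers the relapse hazard, drawing its deaths at the placebo hazard pulls the ratio toward 1. If the two relapse hazards are equal, the draws use the same hazard in both arms and favour neither. The fault is in what the sensitivity analysis means, and it should be corrected before unblinding.

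**What to change.** In SAP 13.1.1, extend the cap to the earliest of the analysis cutoff, the subject's Week 26 and the date of death where one is recorded. An imputed time later than death is then right-censored at death. The draw still starts from the last SAPS-H+D assessment, and the primary analysis keeps its censoring under 5.2.3.

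In SAP 13.1.2, add one supportive analysis of time to adjudicated relapse or death, using the same Cox model, whether or not the study stops at the interim. Any excess of deaths in one arm then counts openly, and the robustness check is not softened by the cap.

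The cost is one clause and one extra Cox run on data already collected. The 75 events, the 178 subjects and the alpha allocation do not change. The downside is that the composite counts deaths unrelated to psychosis, so it should be labelled supportive.

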13.1.2 Sensitivity Analyses

If the study is stopped at the interim analysis, the following sensitivity analyses will be performed:

- Time to relapse based on adjudicated relapse events using data collected up to the study discontinuation date (ITT analysis set). Subjects without any such relapse event will be censored at the last SAPS-H+D assessment prior to the study discontinuation date.
- Time to relapse based on adjudicated relapse events occurring up to the study discontinuation date, plus any additional investigator determined relapse events that occur after the study discontinuation date (ITT analysis set). Subjects without any such relapse event will be censored at the last SAPS-H+D assessment.
- Time to relapse based on investigator determined relapse events using data collected up to the study discontinuation date (ITT analysis set). Subjects without any such relapse event will be censored at the last SAPS-H+D assessment prior to the study discontinuation date.
- Time to relapse based on adjudicated relapse events using the interim analysis dataset and using the Per-protocol analysis set. Subjects without any such relapse event will be censored at the last SAPS-H+D assessment.

If the study is not stopped at the interim analysis, the following sensitivity analyses will be performed:

- Time to relapse based on adjudicated relapse events occurring up to the study discontinuation date, plus any additional investigator determined relapse events that occur after the study discontinuation date (ITT analysis set). Subjects without any such relapse event will be censored at the last SAPS-H+D assessment.

- Time to relapse based on investigator determined relapse events using data collected up to the study discontinuation date (ITT analysis set). Subjects without any such relapse event will be censored at the last SAPS-H+D assessment prior to the study discontinuation date.
- Time to relapse based on adjudicated relapse events occurring up to the study discontinuation date using the Per-protocol analysis set. Subjects without any such relapse event will be censored at the last SAPS-H+D assessment prior to the study discontinuation date.

The same Cox regression model as described in [Section 13.1](#) will be used for each of the sensitivity analyses. The results will be presented in a summary table similar to that described for the primary efficacy analysis. The estimated HRs with corresponding 95% CIs from the primary efficacy analysis and the sensitivity analyses will be presented in a forest plot.

13.2 Key Secondary Efficacy Analysis

The key secondary endpoint is time from randomization to discontinuation from the double-blind period for any reason (other than termination of the study by the sponsor). The hypotheses are stated in terms of the hazard ratio, $HR = \lambda_{PIM} / \lambda_{PBO}$, where λ_{PIM} and λ_{PBO} denote the hazard rates of discontinuation from the double-blind period for any reason (other than termination of the study by the sponsor) for the pimavanserin group and the placebo group, respectively.

The null hypothesis for the key secondary endpoint is: $HR = 1$

The alternative hypothesis for the key secondary endpoint is: $HR \neq 1$

The key secondary efficacy endpoint will be analyzed using the same Cox regression model described for the primary efficacy endpoint. The null hypothesis for the key secondary efficacy endpoint cannot be rejected unless the null hypothesis for the primary efficacy endpoint has been rejected. Adjustment of stopping boundaries for the key secondary endpoint analysis to account for multiple endpoints and group sequential testing is described in [Section 16](#).

The estimated HR, SE, 95% confidence interval, and p-value obtained from the Cox regression model will be presented. The algorithm for censoring of subjects who completed

the 26-week double-blind period without experiencing a relapse event, or who administratively exited the study due to study termination by the sponsor, or who were ongoing at the time of database cutoff is described in [Section 5.2.4](#). The number and percentage of subjects having the following possible reasons for censoring will be tabulated for each treatment group:

- Completed Week 26 without relapse;
- Termination of the study by the sponsor (for the final analysis only);
- Ongoing at the time of the interim database cutoff (for the interim analysis only).

Kaplan-Meier curves of time from randomization to discontinuation from the double-blind period for any reason (other than termination of the study by the sponsor) will be presented for each treatment group. In addition, Kaplan-Meier probability estimates of median survival and at the double-blind Weeks 4, 8, 12, 18, and 26 along with pointwise 95% confidence intervals will be provided. The confidence intervals will be calculated using a log-log transformation and Greenwood's variance formula.

The number and percentage of subjects meeting the following discontinuation reasons for the double-blind period will be tabulated for each treatment group:

- Relapse of hallucinations and delusions associated with dementia-related psychosis adjudicated by the IAC;
- Adverse event;
- Death;
- Non-compliance with study drug;
- Used of prohibited medications;
- Physician decision;
- Protocol violation;
- Pregnancy;
- Subject withdrew consent;
- Lost to follow-up;
- Other.

